#### **4.1 Inclusion Criteria**

Nurse care managers must meet all of the following inclusion criteria in order to be enrolled in the study:

- Actively providing care management services within the Partners HealthCare iCMP program
- Ability to understand study procedures and to comply with them for the entire length of the study.
- Nurse care managers will be considered subjects for the structured interview component of the pilot, with a waiver of documentation of consent

PWD must meet all of the following inclusion criteria in order to be enrolled in the study:

- Medicare beneficiary aligned to the Partners Medicare ACO
- ICD-10 diagnosis code consistent with dementia in Medicare claims between August 1, 2019 and July 31, 2020 (excluding diagnoses for diagnostic testing services)
- Actively engaged in care management services with a nurse care manager enrolled in the study
- Must be at least 18 years old or older

Caregivers must be identified by the iCMP care manager or in the PWD health record as next of kin, health proxy, guardian or primary paid caregiver or by the PCP, must speak English or Spanish, and must be at least 18 years old or older.

#### **4.2 Exclusion Criteria**

Nurse care managers meeting any of the following criteria will be excluded from the study:

- Fewer than 6 months of employment as an iCMP nurse care manager

PWD meeting any of the following criteria will be excluded from the study:

- Permanent resident of long-term care or deceased at the start of the study

Caregivers of PWD meeting any of the following criteria will be excluded from the study:

- Preferred language other than Spanish or English

- lives out of the country
- unclear relationship with PWD

#### 4.3 Study Enrollment Procedures

- The investigative team has presented this study to iCMP leadership prior to funding. The study team will attend an iCMP operations team meeting to discuss the Care Ecosystem training and expectations for participation in training. Calendar year 2019 data will be used to determine the percentage of minority / lowest SES patients within the practices each care manager serves. The study team will collaborate with iCMP leadership to identify 30 nurses, prioritizing nurses who serve the most disadvantaged practices. These nurses will be randomly assigned to either early or delayed training. An e-mail co-signed by the investigator leading the training and iCMP leadership will be sent to the selected nurses informing them of their training date. Limitations in funding do not allow for training of all 87 nurse care managers within this pilot.
- Nurses will be asked to complete an assessment of baseline dementia care knowledge and skills prior to their training.
- Patients who actively receive care management from the 30 identified nurses and who have a diagnosis of dementia within Medicare claims data will be identified as PWD for this study. We will leverage existing data within EPIC to identify caregivers for these PWD.
- Preliminary examination of the structured fields within Epic that are used to house information on caregivers suggests that we will likely need to develop alternative methods, including review of notes, for identifying caregivers.

### 5 STUDY INTERVENTIONS

#### 5.1 Interventions, Administration, and Duration

Following IRB approval, the intervention will include three distinct phases:

- (1) **Developing an adaptation of CareEco training through feedback from a task group.** The CareEco model will be adapted for iCMP teams with input from a taskforce consisting of recently retired highly experienced iCMP nurse care managers, an iCMP medical director, a dementia expert, a pharmacist, and an active caregiver. The taskforce will provide information on current care management practices for PWDs and their caregivers and guide the development of 1) the adapted CareEco training, and 2) the needs-based protocols provided by CareEco. We anticipate that adaptation of the training will involve elimination of clinical content already well known by care managers and enhancement/refinement of content (i.e., management of behavioral symptoms, strategies to reduce caregiver stress) identified by the workgroup as an observed need of iCMP nurse care managers. For example, nurse care managers currently receive training on serious illness conversations, and advance care planning and documentation; these modules in the CareEco training will therefore be truncated. The current training content includes 23 6-minute videos and

hands-on practical training. Based out our review of these videos, the number of these videos will be substantively reduced; a 1-day in-person training will be planned to address hands-on, practical skills-based training needs. Revision of the protocols will be informed by current iCMP workflows and EMR documentation strategies. This phase will occur during the first three months of the project.

- (2) **Training iCMP nurse care managers in the adapted version of CareEco.** Prior to the 1-day in-person training, the care managers will engage in approximately 60 minutes of e-learning of the abbreviated video training. The virtual training through video technology (secure Zoom platform) will occur all in one day and will address communication skills, the use of the CareEco protocols, documentation expectations and workflow concerns. For their involvement, iCMP care managers will receive a stipend and CEU credits. On a weekly basis, the intervention team will offer an hourly check-in to address any questions that arise. The iCMP nurse care managers will also have access to a dementia care expert, in addition to their pre-existing social work and pharmacy team. The intervention team will monitor for intervention fidelity and work with iCMP nurse care managers if deviation from the adapted assessment and protocols are observed. Nurses in the early training cohort will receive their training in month three or month four, while nurses in the delayed training cohort will receive their training at the beginning of month ten.
- (3) **Implementing the adapted CareEco intervention with trained nurse care managers.** The adapted CareEco model will be delivered by the iCMP nurse managers within Partners HealthCare to patients on their panels as clinically appropriate. All care to PWD and their caregivers will be delivered over the phone. The care managers will always address immediate needs first, then screen for common problems and provide personalized support and standardized education using the adapted CareEco Care Plan Protocols; Medications, Safety, Referrals and Caregiver Education, Caregiver Well-being, Behavior Management, and Advance Care Planning. Call frequency will be about monthly but personalized to each dyad's needs and preferences. The study team will offer booster sessions and coaching over the course of the study to iCMP nurse managers who either ask for assistance or who, through chart audits, do not appear to be integrating the training into the care of their PWD. Implementation will occur following completion of training for the nurse care managers randomized to the early training cohort.

## 5.2 Handling of Study Interventions

As described above, the adapted Care Ecosystem training model will consist of dementia care management delivered via phone by nurse care managers to support PWDs and their caregivers.

Due to the pragmatic and embedded nature of this pilot, iCMP nurse care managers will be informed that the intervention will include training on enhanced dementia care management. PWDs and their caregivers will not be informed when their nurse care manager has received CareEco training and will therefore be masked to CareEco training assignment of their care manager.

### **5.3 Concomitant Interventions**

There will be no restrictions on the amount or nature of concomitant interventions for PWDs and their caregivers.

### **5.4 Adherence Assessment**

iCMP nurse care managers will be expected to complete all e-learning modules and attend the entirety of the 1-day in-person training. The intervention team will monitor for intervention fidelity through iCMP data and work with iCMP nurse care managers if deviation from the adapted assessment and protocols are observed.

## **6 STUDY PROCEDURES**

There will be five sources of data to be used in these analyses.

- iCMP Program Data: iCMP collects key process measures including patient status within the program, the number of nurse care manager contacts with the patient / caregiver and community resource requests. Nurses can document caregiver strain and PWD behavioral symptoms in structured fields or in iCMP visit notes. Caregiver depression can likewise be assessed and documented in iCMP visit notes. These data will be used to measure iCMP visit frequency and documentation of key patient and caregiver outcomes in order to assess CareEco implementation fidelity. iCMP program data is captured within Epic and flows directly into the Partners data warehouse, where it is co-housed with clinical and financial data from the Partners electronic health record (Epic) and linked claims data for patients in the Medicare MSSP contract.
- Medicare Claims data will be used to identify iCMP patients with dementia at baseline and over time, and to construct measures of health care utilization and costs.
- Epic clinical data will be used to identify patient caregivers, capture PWD and caregiver outcomes documented in the iCMP note, and identify whether medication reconciliation and serious illness conversations / advance care planning occurred related to the iCMP interaction. In addition, Epic contains structured assessments of caregiver strain and PWD behavioral symptoms. All Epic elements flow to tables within the Partners data warehouse.

For some PWD, outcome measures of caregiver strain and PWD behavioral symptoms have already been integrated into Epic documentation (see data sources above). We will compare EMR-integrated measures with measures derived from the surveys of PWD caregivers to determine the relative completeness and quality of the two data sources with a goal of reducing more resource-intensive primary data collection in future studies.

- Caregiver Survey: All caregivers of PWD (among the eligible cohort) will be asked to participate in a survey at months three (prior to the launch of the CareEco intervention) and nine. A waiver of documentation of consent will be requested for the caregiver survey. The survey will assess caregiver strain and burden, caregiver depression symptoms and behavioral symptoms of dementia and quality of life for the PWD. To streamline identification of caregivers of PWD, study staff will provide nurse care managers with a list of identified PWD and we will review medical records of persons with dementia to identify their caregivers.. Study staff will request that nurse care managers verify the primary caregiver for each PWD. Caregivers of PWD will be sent an invitation letter by mail (caregivers). The invitation letter will be accompanied by a study Fact Sheet about the study and will inform caregivers of their right to refuse participation. The Fact Sheet will address the following points: the research involves no more than minimal risk to the subjects; the waiver or alteration will not adversely affect the rights and welfare of the subjects; the research could not practicably be carried out without the waiver or alteration; and whenever appropriate, the subjects will be provided

with additional pertinent information after participation. If eligible participants refuse, there will be no further contact. If there is no response, we will call to confirm receipt of the letter, re-sending and/or and reviewing content as needed. If participant agrees to be interviewed, the interview will be scheduled. At the time of the interview, the interviewer will again repeat study fact sheet details and proceed if the respondent consents.

- The survey of Caregivers will be administered by phone in both English and Spanish to ensure responses from diverse patient and caregiver populations. Spanish versions will be administered by an experienced native Spanish language health care surveyor with over four years of experience. Care-giver respondents will be offered a \$25 bank gift card, via Forte, in appreciation of their time and effort. Based on our prior experience, we expect 50% to 60% of PWD caregivers will respond. We will assess the extent to which patients with less severe dementia would be able to self-report their symptoms, but for this pilot only caregivers will be surveyed.
- Semi-structured interviews of nurse care managers: All care managers selected for adapted CareEco will be invited to participate (via e-mail) in individual semi-structured quality assurance interviews to debrief on their experiences. The email will address include the following: the research involves no more than minimal risk to the subjects; the waiver or alteration will not adversely affect the rights and welfare of the subjects; the research could not practicably be carried out without the waiver or alteration; and whenever appropriate, the subjects will be provided with additional pertinent information after participation. Nurses will be informed be informed of the potential benefits and risks of participation. Nurses have the right to refuse participation, and decisions to participate will not be linked to employment or be shared with iCMP leadership. This pilot seeks to understand barriers to implementing the CareEco training; information on barriers and challenges will be used for research purposes only and will not become part of personnel files or result in disciplinary actions. No identifiable data from nurse interviews will be shared outside of the study team. Nurses will be asked to approve recording to aid in transcription of the interviews; nurses can refuse recording, but still participate in the interviews. Nurses will receive a small stipend to compensate for their time. Interviews will be performed by phone; a waiver of documentation of consent will be requested for the nurse care manager interviews.

Interviews will be scheduled two months after the launch of the CareEco training (month five). These interviews will be conducted in care manager offices or by telephone or a video technology platform at the convenience of the care manager. The interviews will last approximately 30 to 40 minutes. Research with the iCMP care management staff, conducted by our team in both 2017 and 2018 as part of a PCORI funded study of care management programs, achieved 75% participation rates. Interview domains will include 1) general experience in caring for PWD and their caregivers; 2) experience in direct outreach to caregivers and patients (including identifying the most knowledgeable or engaged caregivers); 3) perceptions of services most needed and most difficult to arrange for patients with dementia and their caregivers; 4) assessment of the adequacy of training as adapted to the iCMP context; 5) recommendations for further adaptation of the CareEco model, and 6) among care managers not participating in the training, implementation

barriers, including contextual factors, fit and overarching issues that impacted non-participation.

The following table summarizes the measures that will be used in this study.

Variable	Source	Primary or secondary outcome	Description
ED visits	Medicare Claims data	Primary	ED visits per member per month over 6 months; Feasibility of collection (Primary objective), difference between early and delayed cohorts (secondary objective)
Service utilization and costs	Medicare Claims data	Secondary	Hospitalizations, Observation stays, urgent visits, total medical expense; Feasibility of collection (Primary objective), difference between early and delayed cohorts (secondary objective)
Documentation of advance care planning	Epic	Secondary	
Documentation of medication review and reconciliation	Epic	Secondary	
Caregiver Depression *	Caregiver survey	Primary and Secondary	PHQ-8 (8 item)
Caregiver strain and burden *	Epic	Primary and Secondary	Caregiver Strain Index presence in Epic and magnitude
Caregiver strain and burden *	Caregiver survey	Primary and Secondary	Zarit Rating Scale (12-item) 
Behavioral Symptoms of Dementia *	Epic and Caregiver survey	Primary and Secondary	NPI-Q (Neuropsychiatric inventory Questionnaire)  presence in Epic and magnitude
PWD quality of life	Caregiver survey	Secondary	QOL-AD (13 items) 
Unmet need and caregiver challenges	Caregiver survey	Secondary	CAHPS  and scaled responses to caregiver self-assessment
iCMP Care in*tensity / quality	Epic	Secondary	Patient contacts, community resource request
Dementia, stage and severity	Caregiver survey	Control variables	Quick Dementia Rating Scale 
Patient and caregiver characteristics	Epic and Caregiver survey	Control variables	Age, race, ethnicity, primary language, area level income, Elixhauser score  caregiver relationship to patient, living proximity to patient

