### Design and Outcomes

We propose a pragmatic randomized quality improvement pilot trial to assess the feasibility and effectiveness of an adapted Care Ecosystem dementia care training for pre-existing nurse care managers who provide care management to high risk patients. We will work with iCMP medical and operational leaders to engage 30 targeted nurse care managers who serve PCP practices with the highest proportions of minority / low SES patients. 15 iCMP nurse care managers will be randomly assigned to receive early Care Ecosystem training and the remaining 15 will be assigned to received delayed Care Ecosystem training. Persons with dementia (PWDs) and their caregivers will not be informed whether their nurse care manager has received Care Ecosystem training, and will therefore be masked to the assignment of their care manager.

Data and outcomes to be included in the QI study will include:

- (1) iCMP key process measures to be extracted from Epic documentation system (patient status, number of contacts between nurse manager and patient and/or caregiver, community resource requests)
- (2) Medicare claims data (health care utilization and costs)
- (3) Epic clinical data (caregiver strain and depression, behavioral symptoms of dementia, medication reconciliation, documented serious illness conversations/advance care planning)
- (4) Semi-structured interviews of nurse care managers
- (5) Surveys of caregivers to augment data captured in Epic clinical data and allow for evaluation of short-term impacts of enhanced training (caregiver strain and burden, caregiver depression symptoms, patient behavioral symptoms of dementia and patient quality of life for PWD).

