### Interventions and Duration

The adapted Care Ecosystem intervention will include three distinct phases:

- (1) Developing an adaptation of Care Ecosystem training and workflows through feedback from a workgroup consisting of recently retired highly experienced iCMP nurse care managers, an iCMP medical director, a dementia expert, pharmacist, and an active caregiver.
- (2) Training of iCMP nurse care managers in the adapted version of Care Ecosystem (e-learning modules and workflows, 1-day in-person training).
- (3) Implementing the adapted Care Ecosystem intervention with trained nurse care managers.
- (4) Booster sessions and process audits to augment intervention fidelity

We will compare the outcomes detailed above between the early training nurse cohort and the delayed training nurse cohort.

We plan to spend the first 3 months of the project collecting feedback and adapting the training. Nurse care managers will be trained at the end of month three. Outcome measures will be collected at the end of month nine. The delayed training cohort will receive training in month ten.

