## **10 DATA COLLECTION AND QUALITY ASSURANCE**

### **10.1 Data Collection Forms**

Primary data collection for PWD and caregivers will include multiple patient-level clinical and claims measures drawn from system records as well as telephone surveys conducted with caregivers of PWD at baseline and follow up. Survey interviewers will be supervised by [name] and will not be aware of whether the PDW's nurse care manager has undergone CareEco training. Data for all patients and caregivers will be maintained in RedCAP; survey data will be entered directly into RedCAP using standard survey procedures. Interviewers will maintain a record of all attempted contacts (Call Log) and their outcomes; a final disposition for each attempted case will be determined when all efforts are exhausted.

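### Epic-recorded caregiver strain and NPI-Q magnitude should not serve as a between-arm effect outcome, because training may change whose scores are recorded

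*Protocol*

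**What the plan says.** **Outcomes and comparison.** The measures table in Protocol section 6 lists caregiver strain with Epic as source, described as "Caregiver Strain Index presence in Epic and magnitude" and labelled both primary and secondary. Behavioural symptoms, measured by "NPI-Q (Neuropsychiatric inventory Questionnaire" and also described by presence in Epic and magnitude, carry the same label, with Epic and the caregiver survey as sources. The table's ED row shows what the two labels mean: feasibility of collection is the primary objective, and the early-versus-delayed difference is the secondary one. The Précis (Design and Outcomes) includes among the study's data and outcomes "Epic clinical data (caregiver strain and depression, behavioral symptoms of dementia, medication reconciliation, documented serious illness conversations/advance care planning". Its Interventions and Duration section adds: "We will compare the outcomes detailed above between the early training nurse cohort and the delayed training nurse cohort". Protocol 9.4 makes training assignment the main predictor in every model.

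**Who records.** Section 6 says: "Nurses can document caregiver strain and PWD behavioral symptoms in structured fields or in iCMP visit notes". It adds that such measures are already in Epic for some patients only, and that documentation of key patient and caregiver outcomes is used to assess implementation fidelity.

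**What training covers.** Under Protocol 5.1 the training "will address communication skills, the use of the CareEco protocols, documentation expectations and workflow concerns". Trained nurses address immediate needs, "then screen for common problems and provide personalized support and standardized education using the adapted CareEco Care Plan Protocols"; those protocols include caregiver well-being and behaviour management. Chart audits identify nurses who do not appear to be using the training, and they are offered coaching.

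**The other source.** Caregivers are surveyed at months 3 and 9 (Protocol 9.3). Protocol 10.1 keeps interviewers unaware of whether the patient's "nurse care manager has undergone CareEco training".

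**The concern.** A mean among recorded cases is a randomized comparison only if being recorded is unaffected by assignment, or is unrelated to the score. Here recording is optional, it is done by someone who knows the assignment, and the protocol treats it as a sign that the intervention was delivered. If training widens recording, the two recorded subsets differ in make-up even when training has no effect on strain or behaviour. Wider recording may bring in milder cases and lower the trained-arm mean. Closer probing may raise it.

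Two later uses are at stake. Protocol 9.2 wants the pilot to supply effect sizes for a full-scale study, and section 6 hopes to replace some survey collection with Epic measures. A spurious Epic difference, or a masked real one, would mislead both.

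**Working it through.** **1. The plan's own figures.** Protocol 9.3 expects 75 caregivers per arm at each survey and 37 at both. With 150 patients per arm and 50% response, 150 × 0.50 = 75 and 75 × 0.50 = 37.5, so both figures reproduce. No Epic recording rate is stated anywhere.

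**2. Does the plan handle differential recording?**
- Protocol 9.4 adjusts for baseline covariates and may use propensity weights for baseline imbalance. Recording happens after randomization. Baseline adjustment restores comparability only if, within each arm, recording is unrelated to the current score given those covariates. Nothing in the plan supports that.
- The expectation of minimal missing data in Protocol 9.3 covers utilization and costs, care intensity, advance care planning, medication review and contacts. It does not cover these scales.
- SAP 7.3 imputes nothing.

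**3. How large could the selection part be?** This is an illustration; every recording rate and every ρ is an assumption. Scores are standard normal with no true arm difference. A fraction p is recorded, ρ is the correlation between score and propensity to be recorded (the same in both arms), and λ(p) = φ(z₁₋ₚ)/p.

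Bias (trained minus delayed) = ρ × [λ(p_trained) − λ(p_delayed)]

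λ(0.2) = 1.40, λ(0.4) = 0.97, λ(0.6) = 0.64, λ(0.8) = 0.35.

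Example for 20% versus 60% with ρ = 0.5: 0.5 × (0.64 − 1.40) = −0.38 SD.

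False-positive rates come from 4,000 simulated trials with 150 patients per arm and a Welch t-test on recorded cases, ignoring clustering by nurse.

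| Delayed / trained recorded | ρ | Bias (SD) | False positives |
|---|---|---|---|
| 20% / 20% | 0.5 | 0 | 5% |
| 20% / 60% | 0 | 0 | 5% |
| 40% / 60% | 0.3 | −0.10 | about 10% |
| 20% / 40% | 0.3 | −0.13 | about 9% |
| 20% / 60% | 0.5 | −0.38 | about 48% |
| 20% / 80% | 0.7 | −0.73 | about 99% |
| 20% / 60% | 1 | −0.76 | not simulated |

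The sign follows ρ. With ρ = −0.3 the same unequal rates give +0.10 to +0.31 SD. The bias is nil if recording is unrelated to the score, or if it is equal and equally selective in both arms. The model leaves out differences in how nurses score, which would add to or offset these values.

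**4. What the survey can deliver instead.** Power = Φ(d/√(1/n₁ + 1/n₂) − 1.96), two-sided 0.05, ignoring clustering and baseline adjustment; alpha and effect sizes are assumed.

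| Pairs per arm | 0.3 SD | 0.5 SD | 0.7 SD |
|---|---|---|---|
| 37 and 37 (Protocol 9.3) | 25% | 58% | 85% |
| 35 and 28 (SAP 7.1.2) | 22% | 51% | 79% |

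Paired response in the validated cohort was 35/143 = 24% and 28/113 = 25%.

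**The case against.** The strongest reply is that no specified result depends on this comparison. The SAP's only clinical outcome is NPI-Q Distress in survey respondents (SAP 2.3, 7.1.2, 8.2), and it contains no Epic strain or Epic NPI-Q analysis. Protocol 9.3 does not list strain or NPI-Q among the measures that rely on Epic and claims, gives the survey the task of systematic capture, and plans to check Epic against it for completeness and correlation. The NPI-Q row names two sources and does not say that magnitude must come from Epic. All of this stands, and it limits the reach of the point. It does not remove it: the strain row ties magnitude to Epic, the Précis promises the arm comparison, and the SAP's silence does not withdraw it.

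A reader might infer that nurses are taught to administer and record exactly these two scales. The documents do not say so. They describe training in documentation and screening within these domains, and neither instrument is named there.

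A reader might also infer that Epic is the only source for the Caregiver Strain Index. The table suggests this, but Protocol 6.2.2 puts that index in the survey battery, while the table gives the 12-item Zarit scale as the survey strain measure.

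Finally, the survey is not free of selection: about a quarter of the validated cohort gave paired responses. Similar rates in the two arms are reassuring but do not show equal selectivity.

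**Conclusion.** The point holds as a risk of bias confined to one use: Epic magnitude as a between-arm effect, clearly planned for the Caregiver Strain Index and, on the natural reading, for NPI-Q. It rests on three documented features: optional recording, nurses who know their own training status, and training and audit directed at documentation.

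It would be tempting to say that the Epic comparison is biased by a stated amount or favours the intervention. The documents do not support that. Bias requires recording to differ by arm, in rate or in selectivity, and to depend on severity, and neither is reported. The range of about 0.1 to 0.76 SD reflects assumed rates, can take either sign, and includes nil under the conditions given above. Nor does the point reach the SAP's NPI-Q Distress result. Epic presence remains legitimate as a feasibility and fidelity measure.

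**What to change.** In the Protocol section 6 table:
- Keep Epic presence of the Caregiver Strain Index and NPI-Q as a feasibility and fidelity outcome, and report recording rates by arm.
- State that between-arm effect estimates of strain and NPI-Q magnitude come from the masked-interviewer survey only.
- Reserve Epic magnitude for the Epic-versus-survey comparison already planned in sections 6 and 9.3, and label any summary of it by arm as descriptive.
- Reconcile the survey strain instrument: Zarit in the table, Caregiver Strain Index in section 6.2.2.

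The edit is small and discards no data. The real cost is precision, because effect estimates then rest on about 37 planned pairs per arm (35 and 28 in the SAP), with roughly even odds of detecting 0.5 SD. The loss relative to Epic is smaller than it looks: Protocol 9.4 adjusts for dementia stage and severity, which the table takes from the caregiver survey, so without imputation an adjusted Epic model would also be limited to survey respondents. Survey non-response should be reported by arm beside the estimates.
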